In Depth Proteomics of colonic mucosal biopsies in duplicate by a label-free LC-MS/MS method (see letter of support from [name] Ph.D., Proteomics Core, Mayo).

Extraction and separation: Proteins from the biopsy will be extracted in SDS buffer containing protease inhibitors using a bead beater to disrupt tissue. Extracted proteins will be run on a gel, proteins separated by size, segmented, and in-gel trypsin digested to obtain peptides to compare across samples.

Liquid chromatography is used to load peptide sample onto a C8 cartridge, which is then placed in-line with a C18 analytical column. Peptides are sorted by ionic strength using a mobile phase gradient of acidic low to high organic solvent, eluted off the column, captured into mass spectrometer (MS) via electrospray ionization, followed by data dependent ms/ms data for peak identification. D. We also have access to single reaction monitoring (SRM) mass spectrometry on QExactive and triple quad instruments in the Proteomics Core for more accurate quantification of proteins if necessary.

Data analysis from high resolution MS will use MaxQuant, a quantitative proteomics software to compare high resolution MS data. Database searching within MaxQuant assigns amino acid sequence to peptides and assembles peptide information back to proteins. Quantified values of proteins between groups are compared.

Biological Samples Collected

1. **Venous Blood Sample** (fasting) will be collected for **serum FGF19 and C4. Venous blood DNA will be stored for future genetic studies.**
2. **Fecal Sample for Fecal Organic Acids:** Gas chromatography-mass spectrometry for SCFA in stool and HPLC tandem MS for total and individual fecal BAs. Samples will now be a random stool sample without a required dietary change unless they have not had a qualifying diagnosis of BAM as noted in the Research Plan below. Samples will then be processed for total fat (routine van de Kamer method at Mayo Medical Laboratory), **total BAs**, and **primary and secondary BAs** [by LC/MS as previously described from our lab (56)], and **SCFA by GC-MS**
3. Additional **stool** and rectosigmoid **mucosa samples** will be **stored for future microbiome studies.**

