Human subjects and design: 30 IBS-D patients with BAM will be randomized (15/group) in 4-week double-blind, parallel-group trial to Colesevelam, 1.875g b.i.d. or placebo. Patients will be stratified on gender and BMI; we anticipate 90% female and 75% BMI >30kg/m².

[figure not shown]
Experimental procedures: Effects of colesevelam/placebo on symptoms (daily stool diaries), as well as colonic transit, fecal bile acid and fat excretion and fasting serum C4 and FGF-19, intestinal permeability and TJ expression in rectosigmoid mucosal biopsies at baseline and at end of 28 days' treatment.

Primary endpoints: 1. Bowel movements/week; 2. Stool consistency based on Bristol Stool Form Scale, BSFS.

Secondary endpoints: 1. Quantitative total fecal BAs; 2. Proportion of secretory BA (CDCA, DCA) in stool; 3.

Fasting serum C4 and FGF-19 levels; 4. Colonic transit, geometric center at 24 and 48 hours; 5. Intestinal and colonic permeability (mannitol, lactulose excretion); 6. TJ expression in rectosigmoid mucosa.

Colesevelam Study Design

This study consists of ten visits to Mayo Clinic at the Charlton 7 Clinical Research Trials Unit (CRTU). Some of the visits can be combined.

Visit 1 (Screen visit) Volunteers will be asked to come to the Charlton 7 to review and sign this informed consent form and all have all their questions answered. This visit will require about 90 minutes.

- **QUESTIONNAIRES:** Volunteers will be asked to complete two questionnaires.
 1. Bowel Disease Questionnaire, which asks questions about their bowel symptoms
 2. Hospital Anxiety and Depression Inventory, which asks about any anxiety or depression they are currently feeling
 3. Quality of Life Questionnaire, which ask you how your bowel symptoms are affecting your life
 4. Symptom Checklist, which ask you about any symptoms you are currently feeling
- **VITAL SIGNS, HEIGHT AND WEIGHT:** A nurse will take your height, weight and vital signs (pulse, blood pressure, respiration rate and temperature).
- **HISTORY AND BRIEF PHYSICAL EXAM:** A study physician will review their medical history, current medications and supplements and perform a physical exam.
- **POSSIBLE BLOOD DRAW:** A small amount of blood may be taken if the study physician determines that blood tests need to be run to see if they qualify for the study. Such as serum alphaC4 or FGF19.

If the study physician finds the volunteer eligible for the study, they will be asked to participate in the rest of the study.

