- **STOOL COLLECTION:** You will be given a stool kit and will be asked to return a stool sample before your Flexible Sigmoidoscopy.
- If the patient has not had previous qualifying FGF19, C4, primary to total fecal bile acids in the past, then fasting serum blood work for FGF19 and C4 will be completed at the Screen visit. A 48 hour stool

test to evaluate for primary and total fecal bile acids will be conducted first. The remaining study examinations, abbreviated colonic transit test, permeability test, random stool sample, flexible sigmoidoscopy, and gallbladder ultrasound will be postponed by at least one week.

Visit 2 (Pretreatment testing) Participants will be asked to report to the desk on Charlton 7 after an 8 hour fast (no food/drink, a small amount of water is OK), and the avoidance of artificial sweeteners 48 hours before and during the permeability testing (Visits 2-3). The visit should take approximately 45-60 minutes.

- **PREGNACY TEST**, if needed: A urine sample will be collected for a pregnancy test from women who can get pregnant if it was not done within 48 hours of this study day. The results of this test must be negative in order for participants to continue the study.
- **FASTING BLOOD DRAW**: Participants will be asked to give a small amount of blood for DNA, serum alpha C4 and FGF19 testing if not done previously.

DIARY RETURN: Participants will be asked to return the completed 7-day Pretreatment Diary.

- **ABBREVIATED COLONIC TRANSIT TEST/Permeability test**: Participants will be asked to swallow a small capsule containing a small amount of a radioactive substance with a liquid containing a small amount of naturally occurring sugars: lactulose and mannitol. The sugars allow the measurement of the permeability of the small intestine and colon. The participants will be instructed to have breakfast one hour later.

VISITS 3-5 MAY BE COMBINED

Visit 3 (24 hour image) Participants will be asked to report to the desk on Charlton 7 (fasting required) approximately 24 hours after they ingested the capsule containing radioisotope during Visit 2. Ultrasound measurement can be performed before or after the 24 hour image is obtained. The ultrasound gallbladder measurement should take ~ 10-15 minutes. This visit should take approximately 25 minutes.

Visit 4 (Flexible sigmoidoscopy) [OPTIONAL] Participants will be asked to report to the desk on Charlton 7 (no fasting required). The visit should take approximately 75 minutes.

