- **ENEMA**: Participants will need to prepare the colon for the sigmoidoscopy by means of a tap water enema at the CRTU. A CRTU nurse will give a tap water enema. Two enemas may be given if needed.
- **FLEXIBLE SIGMOIDOSCOPY WITH BIOPSIES**: A sigmoidoscopy is a lower endoscopy that uses a flexible endoscope to visually inspect the lining of the sigmoid colon. Several biopsies of the lining of the colon will be removed for examination under a microscope, TJ protein expression, proteomics and RNA sequencing.. No sedation is needed. The nurse will review information regarding post-endoscopy care and the participant will be dismissed.

Visit 5 (Study Medication pickup) Participants will be asked to report to the desk on Charlton 7 (no fasting required).The visit should take approximately 15-30 minutes.

- **PREGNACY TEST**, if needed: A urine sample will be collected for a pregnancy test from women who can get pregnant if it was not done within 48 hours of this study day. The results of this test must be negative in order to continue the study.
- **STUDY MEDICATION**: The nurse will dispense a 5 week supply of the Colesevelam/placebo and instruct participants to take 3 tablets orally twice daily with lunch and supper.
- **SINGLE RANDOMSTOOL SPECIMENS**: Returned as instructed
- **DIARIES RETURN**: Participants will be asked to return the completed 7-day Pretreatment Bowel diary
-

TREATMENT: Participants will take 1875 mg (3 tablets [625 mg/tablet]) of the medication orally twice daily with lunch and supper for 4-5 weeks. They also will be asked to complete the following visits after 21 days of treatment with the treatment fat diet and stool collections completed after the transit/permeability and flex sig/biopsy tests. A separate stool sample collection kit will be provided on Visit 6 to be returned before the flexible sigmoidoscopy. No special diet is required with this particular stool collection.

Note: Treatment Bowel diary will not be completed by participants during high fat diet.

Visit 6 (Treatment testing) Participants will be asked to report to the desk on Charlton 7 after an 8 hour fast (no food/drink, a small amount of water is OK). And the avoidance of artificial sweeteners 48 hours before and during the permeability testing (Visits 6-7). This visit will require about 9-10 hours total.

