Visit 7 (24 hour image) Participants will be asked to report to the desk on Charlton 7 (fasting required) for the 24 hour image. Ultrasound measurement can be performed before or after the 24 hour image is obtained. The ultrasound gallbladder measurement should take ~ 10-15 minutes. The visit should take approximately 25 minutes.

VISITS 8 AND 9 MAY BE COMBINED

Visit 8 (48 hour image and urine collection return) Participants will be asked to report to the desk on Charlton 7 (no fasting required) to drop off their 8-24 hour urine collection and have the 48 hour image taken. The visit should take approximately 10 minutes.

Visit 9 (Flexible sigmoidoscopy) [OPTIONAL] Participants will be asked to report to the desk on Charlton 7 (no fasting required). The visit should take approximately 75 minutes.

- **ENEMA**: same as Visit 4
- **FLEXIBLE SIGMOIDOSCOPY WITH BIOPSIES**: same as Visit 4

Visit 10: End of Study:

- **DIARIES RETURN**: Participants will be asked to return the completed Treatment Bowel diary
- **MEDICATION RETURN**: On the last visit participants will be asked to return any unused medication.

Statistical analyses: Effects of treatment will be compared (using Intention-To-Treat principles) using ANCOVA with BMI, gender, baseline colonic transit and baseline fecal BA excretion as covariates.

November 1 2018: at least 75% of the participants will have completed all study procedures. We plan to complete an interim analysis in order to submit an abstract for a national gastroenterology meeting in May 2019. We anticipate completing all studies in all participants by the time the data need to be presented. At that time, we shall present the data from the ENTIRE patient cohort; that analysis will be used for the one full manuscript emanating from these data.

A senior statistician will review the interim analysis results and analyze the data related to the previously determined primary endpoints. All members of the study team and the investigative team will remain blinded to treatment arm assignment and treatment arm results until the completion of the study. Thus, this would not affect the p value when the study is completed.

Statistical power: Based on our previous open-label study, the proposed sample size (15 per group) has

Response	Mean (SD)	Detectable Δ
#Stools /week	15.1 (6.6)	7.00
Stool Form (BSFS 1-7 scale)	4.4 (1.0)	1.06
Total Fecal BA excretion μ moles/48h	3496 (2456)	2650
Fecal Fat g/24h	6.8 (3.1)	3.30
Serum C4 ng/mL	72.3 (4.3)	45

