~80% power (2-sided $\alpha=0.05$) to detect clinically relevant effect sizes in stool frequency and form (expressed as detectable difference [Δ] in 2 groups: in **Table 3: Detectable differences based on 80% power.**

Anticipated results and significance: Colesevelam will reduce stool frequency, decrease stool consistency and slow colonic transit in IBS-D with high BA

excretion.

Precautions and alternative approaches:

1. The RCT has sufficient power based on directly relevant open-label trial data with same drug and disease.
2. Other agents that reduce hepatic BA synthesis and are in development will be alternatives for BA sequestrants, e.g. FXR agonists, FGF-19 analogs.

PLANNED ENROLLMENT REPORT

Comments: 30 patients IBS-D with BAM

Racial Categories	Ethnic Categories				Total
	Not Hispanic or Latino		Hispanic or Latino		
	Female	Male	Female	Male	
American Indian / Alaska Native	1	0	0	0	1
Asian	2	1	0	0	3
Native Hawaiian or Other Pacific Islander	0	0	0	0	0
Black or African American	2	1	0	0	3
White	13	7	2	1	23
More Than One Race	0	0	0	0	0
Total	18	9	2	1	30

Inclusion of Children

Children, 18-21 years of age, and adults 21 years or older will be eligible for participation in the study as active participants or as healthy controls. However, children below 18 years of age will be excluded, since there are differences in the criteria of diagnosis in adults and children, and insufficient quantitative pediatric data on the traits to be analyzed in order to assess the phenotypes of IBS, e.g. transit, permeability, etc.

Inclusion of Women and Minorities

In advertisements for patients and healthy subjects, we shall specifically solicit participation of women and minorities. We anticipate that there will be a majority of whites and representation of blacks and Asians, consistent with the ethnic constitution of communities in southeastern Minnesota, which is approximately 90% Caucasian, 5% Southeast Asian, and 5% other minorities. The prevalence of IBS among whites, blacks and Hispanics in the U.S. is very similar.

Consideration of Sex as a Biological Variable

We plan to recruit approximately 2 females to one male patient for these studies. We shall set up special efforts to recruit males with IBS using REDCAP to identify male patients through the electronic health records

(established 17 years ago at Mayo Clinic. Thus, we have identified through search of electronic medical records that there are:

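### The primary ANCOVA leaves out each primary endpoint's own 7-day pretreatment value, a low-cost precision gain if its partial correlation with the outcome exceeds about 0.22

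*Combined protocol and SAP*

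**What the plan says.** The Research Plan names two primary endpoints: "Primary endpoints: 1. Bowel movements/week; 2. Stool consistency based on Bristol Stool Form Scale, BSFS". The design is stated as "30 IBS-D patients with BAM will be randomized (15/group) in 4-week double-blind, parallel-group trial".

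The Statistical analyses paragraph gives one model for all endpoints, an intention-to-treat comparison "using ANCOVA with BMI, gender, baseline colonic transit and baseline fecal BA excretion as covariates". No other section adds a covariate, and none says whether the response is the on-treatment value or the change from baseline.

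A pretreatment diary is collected. Visit 2 says "Participants will be asked to return the completed 7-day Pretreatment Diary" and Visit 5, where study drug is dispensed, says "Participants will be asked to return the completed 7-day Pretreatment Bowel diary". The diary's items are not listed, so that it records stool form as well as frequency is an inference. The experimental procedures do take symptoms from daily stool diaries.

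Table 3 gives detectable differences at 80% power: 7.00 stools/week with SD 6.6, and 1.06 BSFS points with SD 1.0, from an earlier open-label study. It gives no correlation between baseline and outcome.

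**The concern.** The covariate list gives two secondary endpoints, colonic transit and total fecal bile acids, adjustment for their own baseline. It gives neither primary endpoint the same treatment. With 15 patients per arm there is little precision to spare, and an endpoint's own pretreatment value is a natural candidate for a prognostic covariate.

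The unstated response matters too. With own baseline in the model, the on-treatment value and the change from baseline yield the same treatment estimate and test. Without it they are different analyses with different power, and the choice is left to the analyst.

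Only precision and this open choice are at stake. Randomisation protects the treatment estimate under either model.

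**Working it through.** **Inputs.** From the documents: 15 per arm, two-sided 0.05, SD 6.6 (stools/week) and 1.0 (BSFS), differences 7.00 and 1.06, four listed covariates. Assumed: the Table 3 SD is the on-treatment SD, and the partial correlation r (given treatment and the four listed covariates) is 0, 0.3, 0.5 or 0.7.

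**Formula.** With N patients, n = N/2 per arm and k covariates:

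- df = N − 2 − k
- SE = SD·√(1 − R²)·√[(2/n)(1 + k/(N − 3 − k))]
- power from the noncentral t distribution

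**Step 1: Table 3.** With k = 0, SE = 6.6·√(2/15) = 2.410, the noncentrality is 7.00/2.410 = 2.905 on 28 df, and power is 80.1%. For BSFS it is 80.0%. Table 3 therefore reproduces as an unadjusted comparison.

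**Step 2: planned model.** With k = 4 and listed covariates that explain nothing, SE = 6.6·√[(2/15)(1 + 4/23)] = 2.611 on 24 df. Power is 73.0%. The 95% CI half-width is 2.064 × 2.611 = 5.39 stools/week, or 0.82 BSFS points.

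**Step 3: add own baseline.** With k = 5, SE = 6.6·√(1 − r²)·√[(2/15)(1 + 5/22)] = 2.670·√(1 − r²) on 23 df.

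| | Planned | r = 0 | r = 0.3 | r = 0.5 | r = 0.7 |
|---|---|---|---|---|---|
| Power, N = 30, listed covariates explain nothing | 73% | 71% | 75% | 83% | 94% |
| CI half-width, stools/week | 5.4 | 5.5 | 5.3 | 4.8 | 3.9 |
| CI half-width, BSFS | 0.82 | 0.84 | 0.80 | 0.73 | 0.60 |
| Power, N = 30, listed covariates explain 16% of variance | 80% | 78% | 82% | 89% | 97% |
| Power, N = 24, listed covariates explain nothing | 60% | 57% | 61% | 69% | 85% |

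Power for the two endpoints agrees to within 0.1 percentage point.

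The N = 24 row is an assumption. A 48-hour baseline fecal bile acid value may not exist for everyone, because the Biological Samples section says "Samples will now be a random stool sample without a required dietary change unless they have not had a qualifying diagnosis of BAM". That would reduce complete cases in both models alike.

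**Step 4: break-even.** On CI width at N = 30, solve (1 − r²)·(23/22)·(2.0687/2.0639)² = 1. This gives r² = 0.048 and r = 0.219. On power, r = 0.217. With 28, 26 and 24 analysed, break-even on power is 0.23, 0.24 and 0.26.

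**Step 5: change from baseline without own baseline.** With equal SDs before and on treatment, the change has SD 6.6·√[2(1 − r)]. If the listed covariates explain nothing, four-covariate power is 58%, 73% and 91% at r = 0.3, 0.5 and 0.7. The on-treatment value gives 73% throughout, so change is the weaker response when r is below 0.5.

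**Check by simulation.** This used 20,000 trials per setting, 10 women and 5 men per arm, a true difference of 7.0 and listed covariates that explain nothing. Planned power was about 75%; with own baseline it was 72%, 77%, 84% and 95%. The mean estimate was 7.0 in every setting. Type I error at r = 0.5 was 5.2% as planned and 5.1% with own baseline. On-treatment and change responses gave identical results once own baseline was included.

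**The case against.** Four points can be made for leaving the plan as it is.

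- **The gain is unknown.** The relevant r is partial, after transit and fecal bile acids, and may be well below the raw diary correlation. At r = 0.3 the gain is 2 power points. This stands, and is why the point is only a suggestion.
- **73% is a pessimistic start.** Randomisation is stratified on gender and BMI. If both are balanced by design, only two covariates add random imbalance: SE = 6.6·√[(2/15)(1 + 2/25)] = 2.50 on 24 df, with power about 76%. If the listed covariates explain 16% of variance it is 80%. The drop from 80% to 73% comes from the listed covariates, not from the omission. This stands too, but it moves both models up together.
- **A missing pretreatment diary could cost more than one degree of freedom.** Under complete-case analysis of the on-treatment value, it removes a patient from the enlarged model only. Against the planned model at N = 30, break-even r rises to 0.30 with one diary missing, 0.37 with two and 0.47 with four. At r = 0.3 with two missing, power is 70.9%. The arithmetic is right, but the documents state neither diary loss nor complete-case deletion, and imputing a missing baseline avoids most of the loss. It is a reason to write a rule.
- **The response may be the change.** At r = 0.7, change already has 91% power, so own baseline adds 3 points rather than 21. At r = 0.3 it adds about 16 (58% to 75%). Under equal SDs the baseline-to-change correlation is √[(1 − r)/2] in size, which stays above 0.22 until r passes about 0.90. Own baseline therefore helps under this reading as well.

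**Conclusion.** The concern holds as a low-cost improvement, not as an error. The omission is plain in the text. Including own baseline changes power from 73% to between 71% and 94% over r = 0 to 0.7, and breaks even near r = 0.22 with 30 analysed. The possible loss is small (about 2 power points at N = 30, about 3 at N = 24) and the possible gain is large (about 10 points at r = 0.5 and 21 at r = 0.7).

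These figures assume that Table 3's SD applies on treatment, that the listed covariates explain nothing unless stated, and that no patient is dropped for a missing pretreatment diary. Confidence is high that own baseline is omitted and low on the size of the gain. Closing the choice between on-treatment value and change is a benefit whatever r turns out to be.

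**What to change.** Amend the Statistical analyses paragraph to name one primary model:

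> Each primary endpoint will be analysed by ANCOVA of the on-treatment value on treatment, gender, BMI, colonic transit at baseline, fecal BA excretion at baseline, and the same endpoint's 7-day pretreatment diary value.

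In the same amendment, state how a missing pretreatment diary is handled (for example, imputing the mean of all patients' pretreatment values, without reference to arm). Also state which seven pretreatment days count, since return is listed at both Visit 2 and Visit 5, and which on-treatment days form the response.

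The cost is one dated amendment and one degree of freedom per model. No new data, visit or patient is needed. The amendment should precede any look at treatment-arm results. The plan says "We plan to complete an interim analysis in order to submit an abstract for a national gastroenterology meeting in May 2019", tied to November 1 2018 with at least 75% of participants complete, so it should be dated before that analysis.

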In view of the radiation exposure, all females of childbearing age will be required to have a negative urine pregnancy test within 48 hours of the radioisotope studies.

ii. Flexible Sigmoidoscopy has very low risk of bowel perforation, estimated at ~1 in 10,000.

To date, these studies have not been associated with any perforation or mucosal damage that resulted in any clinically important issues such as local hemorrhage or abscess formation.

iii. Medications:

No unapproved medications are being tested:

Colesevelam will be used for an unapproved indication, but there is no intention to develop plans to acquire approval to market the medication for the indication IBS-diarrhea with increased fecal BA excretion. Mayo Clinic Research Pharmacy will over-encapsulate commercially available medication, produce identical placebo capsules and will be responsible for maintaining the randomization code and study blinding.

Flexible sigmoidoscopy and rectosigmoid biopsies will be performed without conscious sedation.

iv. Genetic information

Results of the studies will be maintained in summaries in computer-secured files protected by a personal password. In the latter files, participants will be identified only by a 7 digit Mayo Clinic registration number rather than by name to ensure confidentiality. Since genetic information collected is not yet pertinent to clinical practice, the information will not be included in the medical record, but will be maintained in a coded fashion and is accessible only to IRB-approved study personnel. Many of the principles described by Beskow et al. (84) with respect to the exploratory analysis of gene-disease associations apply, so the consent process for genetic analysis will not require exhaustive genetic counseling.

Plans for ensuring necessary interventions to protect participants are included in the data safety monitoring plan (see under 5 below)

Given the prior track record with use of all of the intubations, measurement devices, secure protection of information on genetic information, there is a very high likelihood that the studies will be conducted safely and the participants will be protected from harm.

3. Potential Benefits of the Proposed Research to the Subjects and Others

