Stopping rules report regarding statistical power implications of drop outs and missing data	Yearly	Principal Investigator, Independent Monitor

Subject Accrual and Compliance

- 1) Measurement and reporting of subject accrual, adherence to inclusion/exclusion criteria – Review of the rate of subject accrual, adherence to inclusion/exclusion criteria will occur yearly during the 4.5 year recruitment phase. Review will occur at the end of each recruitment wave to assure that participants meet eligibility criteria and ethnic diversity goals outlined in the grant proposal.
- 2) Measurement and reporting of participant compliance to treatment protocol – compliance will be measured by number of returned tablets at end of treatment phase.

Justification of Sample Size – The application documents the justification of sample size for each specific aim in the proposal.

Stopping Rules – This study will be stopped prior to its completion if adverse effects to the procedures that significantly impact the risk-benefit ratio have been observed

E. **Designation of an Independent Monitor** – [name], M.D. (Mayo Clinic) will serve as independent monitor to perform an independent review of ongoing safety. In accordance with IRB review, we shall ask [name] to constitute an independent DSMB if required. Colesevelam is an approved drug. Since we shall not be applying to FDA to market the drug for a new indication, an IND will not be required for the study.

Safety Review Plan – Study progress and safety will be reviewed monthly (and more frequently, if needed). Progress reports, including patient recruitment, retention/attrition, and AEs will be provided to the Independent Monitor every year. An annual report will be compiled and will include a list and summarization of adverse events. In addition, the annual report will address:

- (1) whether adverse event rates are consistent with pre-study assumptions;
- (2) reason for dropouts from the study;
- (3) whether all participants met entry criteria;
- (4) whether continuation of the study is justified on the basis that additional data are needed to accomplish the stated aims of the study; and
- (5) conditions whereby the study might be terminated prematurely.

The annual report will be signed by the Independent Monitor and will be forwarded to the IRB and the CRTU on an annual basis.

VI. Informed Consent

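### Does an interim analysis run for a meeting abstract damage the final p value?

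*Combined protocol and SAP*

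**What the plan says.** The plan is a single combined protocol and SAP. Its Statistical analyses section expects at least 75% of participants to have finished by 1 November 2018 and gives the purpose of the look: "We plan to complete an interim analysis in order to submit an abstract for a national gastroenterology meeting in May 2019". The work is assigned to one person: "A senior statistician will review the interim analysis results and analyze the data related to the previously determined primary endpoints". On masking, which lasts to the end of the trial, it says: "All members of the study team and the investigative team will remain blinded to treatment arm assignment and treatment arm results until the completion". From this it draws the sentence at issue: "Thus, this would not affect the p value when the study is completed".

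On what will be reported, it anticipates that every patient will be complete by the time of the meeting and continues: "At that time, we shall present the data from the ENTIRE patient cohort; that analysis will be used for the one full manuscript".

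Two other places bear on whether the interim could have consequences, both in the Data and Safety Monitoring Plan. Its Stopping Rules item reads: "This study will be stopped prior to its completion if adverse effects to the procedures that significantly impact the risk-benefit ratio have been observed". Its Safety Review Plan lists topics for an annual report, among them "whether continuation of the study is justified on the basis that additional data are needed to accomplish the stated aims of the study". Separately, the Medications item under Specific Risks and Precautions says that the research pharmacy "will be responsible for maintaining the randomization code and study blinding".

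No boundary or alpha allocation is given for the interim.

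**The concern.** Three things catch the eye.

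- **Purpose against blinding.** An abstract that compares the arms would disclose arm results before completion. An abstract that does not compare them has no need of an analysis by arm. The plan does not say which is meant.
- **The inference.** What protects the error rate of the final test is that the interim has no consequence: it cannot stop the trial, change it or stand as a claim. Blinding is a different property, yet the plan's conclusion is drawn from blinding.
- **Possible leaks.** The annual report asks whether more data are needed. The plan does not state whether the senior statistician sits outside the study team, or how the code reaches that person.

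At stake would be the 5% error rate of the two primary comparisons. Both endpoints (bowel movements per week and stool form) come from patient diaries. If arm-level results became known early, expectation could in principle colour the remaining diaries. A submitted result by arm could also differ from the full-cohort result presented later.

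**Working it through.** **Inputs from the plan.** 30 patients, 15 per group (Human subjects and design); two-sided alpha 0.05 and about 80% power (Statistical power, Table 3); interim with at least 75% complete (Statistical analyses).

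**The plan's own power figure.** Two-sample t test with 28 degrees of freedom and noncentrality δ/(SD·√(2/15)):

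- Stools per week: 7.00/(6.6 × 0.3651) = 2.905, power 0.8006.
- Stool form: 1.06/(1.0 × 0.3651) = 2.903, power 0.8001.

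The stated 80% reproduces.

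**Patients outstanding.** 0.75 × 30 = 22.5, so at least 23 are complete and at most 7 are not.

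**Case A: only the full-cohort test counts.** The interim statistic does not enter the decision, so the error is P(|Z₂| > 1.96) = 0.050 per endpoint. A simulation of 200,000 null trials with t tests gave 0.0498. No adjustment is needed.

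**Case B: either look could stand as a finding at 0.05.** The plan does not provide for this; it is computed only to show what would be at stake. The two statistics are bivariate normal with correlation √(n/30), and the error is P(|Z₁| > 1.96 or |Z₂| > 1.96).

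| Complete at interim | Correlation | Error per endpoint |
|---|---|---|
| 23 of 30 | 0.876 | 0.073 |
| 24 of 30 | 0.894 | 0.071 |
| 27 of 30 | 0.949 | 0.065 |
| 29 of 30 | 0.983 | 0.059 |

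Simulated t tests with 11 or 12 per arm at the interim gave 0.075 and 0.071.

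**Disagreement between the looks at 23 of 30.** Under no effect, (0.0726 − 0.0500)/0.0500 = 0.45 of significant interim results would not be significant in the full cohort. At 80% final power the drift is 1.960 + 0.842 = 2.802. The interim drift is 2.802 × 0.876 = 2.453, which gives interim power 0.689. The verdicts differ in 0.134 (interim not significant, final significant) + 0.023 (the reverse) = 0.157 of trials. This also matters only if an interim verdict is published.

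**Which case does the text describe?**

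| Route by which the interim could matter | What the plan says |
|---|---|
| Team acts on arm results | All team members are blinded to assignment and to arm results until completion |
| Stop for efficacy or futility | No such rule; the only stopping rule concerns adverse effects |
| Annual continuation review | Reviewers are the principal investigator, who is blinded, and the Independent Monitor, whose progress reports are described as covering recruitment, retention and adverse events; no efficacy result is listed |
| Interim result published as the finding | Presentation and the one manuscript use the full cohort |

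Each route is closed or has no text behind it. The plan describes Case A.

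**The case for a change.** The strongest argument for a change is that the plan reaches a true conclusion without stating the condition that makes it true. The full-cohort commitment covers the presentation and the manuscript, not the abstract submitted beforehand, and full completion by the meeting is anticipated rather than promised. A few sentences would settle the matter without adding patients or an alpha adjustment.

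Part of this stands. The abstract's content is undefined, and no sentence says outright that the interim cannot stop or alter the trial.

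The rest is weaker.

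- To call the plan's reason wrong goes too far. People who do not know the arm results cannot stop, extend or modify the trial because of them, so blinding everyone who runs the trial is one way of leaving the interim without consequence. The reasoning is compressed rather than mistaken.
- If the blinding is honoured, the team cannot write arm results into an abstract. The only content consistent with the text is design, baseline or pooled data.
- The continuation item reads as a general monitoring topic, and nothing connects it to the interim.
- Setting one statistician apart from a blinded team is most naturally read as placing that person outside it. How the code is handed over is operational detail.
- A replacement sentence declaring a single 0.05 test would bring its own fault, because there are two primary endpoints and the level would have to be stated for each.

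**Conclusion.** The concern identifies missing detail, not an error in the design. Carried out as written, the plan gives one full-cohort ANCOVA for each primary endpoint with 5.0% two-sided error and no inflation from the interim. The 7.3% figure, and the 45% of null interim findings that would later reverse, belong to a use of the interim that the plan does not provide for.

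This rests on three assumptions: the blinding to arm results holds, the submitted abstract accordingly carries no comparison by arm, and nobody outside the team uses the interim to alter the trial. If the first two failed, individual assignments would still be masked and at most 7 of 30 patients could still be giving diary data. Any effect would be one of group-level expectation, and its size cannot be estimated from the documents.

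A statistician working from this text would fill the gap in the way it already points. New wording would mostly restate the policy and would not alter the analysis or its error rate. No change follows.
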